**Discontinuation Criteria**

Recruitment at the center may be stopped for reasons of particularly low recruitment, protocol violation, and inadequate data recording. Premature termination of this clinical trial may occur because of a regulatory authority

decision, or a change in opinion of the IRB.

The reason for a subject discontinuing from the study will be recorded in the case report form. A discontinuation occurs when an enrolled subject ceases participation in the study, regardless of the circumstances, prior to completion of the protocol. The investigator must determine the primary reason for discontinuation. Withdrawal due to adverse event should be distinguished from withdrawal due to insufficient response. A discontinuation must be reported immediately to the clinical monitor or his/her designated representative if it is due to a serious adverse event. The final evaluation required by the protocol will be performed at the time of study discontinuation. The investigator will record the reason for study discontinuation, provide or arrange for appropriate follow-up (if required) for such subjects, and document the course of the subject's condition. Subjects who discontinue product under study may continue participation in the study. Subjects will be required to maintain the visit schedule and may be eligible to continue participation in the nontreatment phase of the study.

### **Safety Reporting**

#### **Adverse Events**

All observed or volunteered adverse events, or suspected causal relationship to study product, will be recorded on the adverse event page(s) of the eCRF. Adverse and serious adverse events, symptoms thought to be related to tobacco smoking, EC or HnB use, and to withdrawal from nicotine will be recorded and presented as per randomization arm. For all adverse events, the investigator must pursue and obtain information adequate both to determine the outcome of the adverse event and to assess whether it meets the criteria for classification as a serious adverse event requiring immediate notification. For all adverse events, sufficient information should be obtained by the investigator to determine the causality of the adverse event (i.e., study product or other illness). The investigator is required to assess causality and indicate that assessment on the eCRF. Follow-up of the adverse event, after the date of study discontinuation, is required if the adverse event or its sequelae persist.

#### **Serious Adverse Events**

All serious adverse events (as defined below) regardless of study group or suspected relationship to study product must be reported immediately. A serious adverse event is any adverse experience that:

1. Results in death;
2. Is life-threatening;
3. Results in subject hospitalization;
4. Results in a persistent or significant disability/incapacity.

## **Statistical Analysis Plan**

### **Sample size calculation**

We assume that:

- current e-vapor products provide a 25% quitting rate in clinical trials (1,2)
- non-inferiority in quit rates means that the proportion of subjects successfully quitting smoking using the test product is not worse than the proportion of subjects quitting smoking using the alternative or reference product, this difference is allowed a tolerance of 15% (3,4).

For sample size definition, we used the Farrington-Manning Score Test for Proportion Difference, assuming:

- asymptotic normal distribution, upper one-tailed
- alpha 0.05
- nominal power 0.80

Thus:

- Null Proportion Diff. -0.15
- Ref Proportion 0.25
- N per group: 104

Consequently, a total of 220 smokers not intending to quit (110 per each arm) will be recruited.

### **Statistics**

#### **Primary study endpoint:**

Quit rate at 3 months in the experimental (study) group – with respect to reference group – by means a non-inferiority threshold of 15%.

Quit rates will be evaluated on an intention-to-treat basis: subjects known to have failed will be considered as treatment failures in the primary analysis along with subjects lost to follow-up.

#### **Secondary study endpoints:**

Different urinary metabolites will be evaluated at week 4 by means of a descriptive analysis using 95% confidence intervals, adjusted for confounding variables and for the baseline log-transformed level of the biomarker.

#### **Safety assessments:**

Descriptive statistics will be used to summarize the number and percentage of subjects experiencing adverse events

and adverse reactions by study group. Parametric and non-parametric data will be expressed as mean ( $\pm$ SD) and median (and interquartile range [IQR]) respectively. Within-group (from baseline) and between-group differences were evaluated by means of parametric and non parametric statistical tests, for paired and unpaired data, as appropriate. Significance of differences in frequency distribution of categorical variables will be tested by  $\chi^2$  test.

## Data Management Plan

For this study, a web-based Electronic Case Report Form (eCRF), provided by a CRO with expertise in tobacco research studies. This CRO will be used for collecting the data. All the Data Management activities will be carried forward according to the CRO SOPs. Before the study start, the Investigator will be trained on the use of the eCRF functions. He/She will be provided with specific access rights (which can be changed in any time), which allow him/her to enter the system, and a dedicated user's manual. The source data, recorded in the appropriate source documentation at site, will be reported by the Investigator or a designee into the eCRF Database. The data cleaning will be performed by the CRO Data Management team, who will provide the Investigator with all the inconsistencies found through a specific function implemented in the eCRF. The validation of the inconsistencies (change or acceptance) will be made by the Investigator by using the cited function. All the activities related to the data managing will be described in the Data Management Plan (DMP) that will be prepared and maintained for the whole study duration by the Data Management of the CRO. The DMP will also include all the edit check implemented into the eCRF or to be run in batch on the Database.

Before the data freezing, the CRO will code the medical terms. All the activities related to the Database freezing will be described in the DMP. After having frozen the Database, the CRO Data Manager will send it to the Biostatistics Unit for the Statistical Analyses. This activity will also be described in the DMP.

## Publication & Presentation Strategy

Dissemination activities will be performed after clinical study close out.

The study results will be disseminated principally through peer reviewed academic publications, and by way of dissemination events. We will prioritise the use of open access channels in the course of dissemination activities.

At least **3 peer-reviewed open access academic publications** will be submitted within the end of 2018 to high impact scientific journals (indexed on PubMed), about:

- success (efficacy and reduction) rates and tolerability, comparing EC vs HnB;
- tobacco harm reduction values, comparing EC vs HnB;
- product satisfaction, effects on craving and nicotine withdrawal, product preferences, risk perception, subjective and sensorial effects, comparing EC vs HnB.

First of the **dissemination events** will take place after study close out as an international conference held in Catania where final results will be presented. Participation of at least 30 experts from relevant backgrounds, and of international media/journalists is foreseen.

Second and third dissemination events will take place as oral and/or poster presentations on the preliminary and final data to two international congresses/conferences, to present the results to the scientific community and to the general public.

## VERSION HISTORY

Version	Date	Description of the Change(s)
Final 1.0	03 January 2020	First Final version of the document
Final 1.1	04 June 2020	Section 4: PP population definition added. Section 5.2: description of derived datasets added. Sections 6.8 and 7.5: VO2MAX analysis for the Step Test added. Section 7: specification of the analysis populations added Section 7.1: definition of "Continuous Quitter" added Section 7.2.1: Russell Standard analysis included Section 7.2.2: section modified Section 8: specification of the analysis populations added Appendix 1: Index of the TFLs fixed All the mock tables fixed.
Final 2.0	08 July 2020	Section 4: PP V7 population definition added. Section 9.7: new section included. Appendix 5: DRM Minute included.

## 1 INTRODUCTION

This Statistical Analysis Plan (SAP) is based on the study Protocol Final Version (dated September 26, 2017). The main objective of this document is to provide guidance for the production of the analyses of all the variables included in the Database of the study which will be frozen when the last data is validated in accordance with the Fullcro's SOPs.

This document will also provide guidance for the production of the Statistical Report (SR), the in-text tables, the in-text listings and the Tables/Figures/Listings (TFLs) which will be part of the SR as Appendices (they will regard the data of all patients and all variables included in the Database).

The Statistical analysis will begin once the data validation is complete and will proceed according to this plan. In case of deviations from this SAP, explanations in the Statistical Report (SR) will be provided.

This document refers to the analysis of all the variables included in the Clinical Data Base.

All details on the decisions made during the Data Review Meeting (DRM) will be described in an *ad hoc* section in Version 2.0 of the present document that will be produced before the Database freezing.

### 1.2 List of abbreviations and acronyms

AE	Adverse Event
BoBE	Biomarkers of Biological Effects
BP	Blood Pressure
DRM	Data Review Meeting
EC	Electronic Cigarette
eCO	Exhaled breath Carbon monoxide
GCP	Good Clinical Practice
HnB	Heat-not-Burn
HR	Heart Rate
ITUQ	Intent to use questionnaire

	
e-CIG VS. IQOS Statistical Analysis Plan Version 2.0
	
Doc code: BIOSTAT.SAP.02

		
Pag. 6 of 115

LOCF Last Observation Carried Forward

mCEQ Modified Cigarette Evaluation Questionnaire

PT Preferred Term

SR Statistic Report

SAE Serious Adverse Event

SOC System Organ Class

	e-CIG VS. IQOS Statistical Analysis Plan Version 2.0	Doc code: BIOSTAT.SAP.02
		Pag. 7 of 115

## 2 STUDY DESCRIPTION

### 2.1 Introduction

This is a 12-weeks, open label, non-inferiority trial comparing HnB products vs. ECs in terms of efficacy, adoption rate and acceptability, tolerability, and tobacco harm reduction in healthy smokers, not motivated to quit, randomized (1:1) to switch to one of these products. Evaluation of efficacy, adoption rates, acceptability and tolerability will be also recorded at 24 weeks (follow-up).

### 2.2 Study Objectives

The primary objective of this study is to compare the efficacy of HnB and EC, in terms of quit rates at week 12, by self-reporting abstinence from classic cigarette [validated by an Exhaled breath Carbon monoxide (eCO) measurement  $\leq 10$ ppm].

The secondary objectives are:

- 1) to compare the smoking reduction derived from the use of HnB and EC, intended as a 50% reduction in the number of conventional cigarette/day at week 12, defined through self-reporting;
- 2) to compare the adoption rate, and adherence to product use [by collecting (empty) refill bottles and used heatsticks on a daily basis, verified by a study diary filled daily by the subject];
- 3) to compare the acceptability of HnB and of EC, through the assessment of product satisfaction, risk perception, effects on craving and nicotine withdrawal, product preferences, subjective and sensorial effects by:
  - a) Modified Cigarette Evaluation Questionnaire (mCEQ) adapted for EC and HnB users;
  - b) three of 8 items of "Smoking Cue Appeal" adapted for EC and HnBusers;
  - c) "Intent to use questionnaire" (ITUQ) – items 4-6;
  - d) PRI-P CC Perceived Health Risk scale (for classic cigarette)
  - e) PRI-P RRP Perceived Health Risk scale (for reduced risk products)
  - f) percentage of choice of a particular subtype of heatstick (HnB) or e-liquid.
- 4) to compare the tolerability of HnB and EC, in terms of: self-reported adverse and serious adverse events by study participants, vital signs (BP, HR and body weight) measurements.
- 5) to compare the tobacco harm reduction between HnB and EC, in terms of:
  - a) changes in Biomarkers of Biological Effects (BoBE) such as: eCO in the exhaled breath (i.e. eCO), step test values;

	
e-CIG VS. IQOS Statistical Analysis Plan Version 2.0
	Doc code: BIOSTAT.SAP.02
		Pag. 8 of 115

b) measurement of 14 selected Biomarkers of Exposure (BoE) in spot urine samples of study participants:

1 tobacco-specific nitrosamine, total NNAL (NNK); 8 volatile organic toxicants (derivates of mercapturic acid, MA): 2-hydroxyethylmercapturic acid (HEMA) also known as ethylene oxide, 2-hydroxy-3-butenyl- mercapturic acid and isomers (MHBMA) also known as 1,3-butadiene, 3-hydroxy-1-methyl propyl- mercapturic acid (HMPMA) also known as crotonaldehyde, 3-hydroxypropylmercapturic acid (3-HPMA) also known as acrolein, S-phenylmercapturic acid (S-PMA) also known as benzene, 2-carbamoylethylmercapturic acid (acrylamide mercapturic acid (AAMA) also known as acrylamide (AAMA and GAMA), 2-cyanoethylmercapturic acid (CEMA) also known as acrylonitrile, 2-hydroxypropylmercapturic acid (2-HPMA) also known as propylene oxide; 4 polycyclic aromatic hydrocarbons: naphthalene, fluorine, phenanthrene, pyrene (1-OHP); cotinine; creatinine.

c) self-perception of "Tobacco Harm Reduction process" through changes in quality of life scores (EQ-5Dquestionnaire);

6) to compare the reliability of HnB and EC, in terms of incidence and kind of malfunctioning events, through self-reporting.

### 2.3 Study Design

This is a 12-weeks, open label, non-inferiority trial.

### 2.4 Product Administered

Participants randomized in study group with HnB (group A) will receive one iQOS kit and a 12 weeks supply of heatsticks; those in study with EC (group B) will receive one JustFog Starter Kit and a 12 weeks supply of e-liquids.

### 2.5 Study Plan

This study has been structured considering a Screening visit (V0), a Baseline visit (V1), a week 1 visit, a week 2 visit, a week 4 visit, a week 8 visit, a week 12 visit. A prospective evaluation of efficacy, adoption rates, acceptability and tolerability will be also recorded at 24-weeks, through a follow-up visit (V7).

## 3 SAMPLE SIZE

	e-CIG VS. IQOS Statistical Analysis Plan Version 2.0	Doc code: BIOSTAT.SAP.02
		Pag. 9 of 115

Sample size determination (better detailed in the study protocol) for no-inferiority testing is based on the assumptions that:

- 1) expected quit rates based on most recent EC literature is about 20-25% and
- 2) that differences in quit rates between products under investigation should not exceed 10-15% (as per non-inferiority definition).

For sample size definition, Farrington-Manning Score Test for Proportion Difference was used, assuming:

- asymptotic normal distribution, upper one-tailed
- alpha 0.05
- nominal power 0.80

Thus:

- Null Proportion Diff. -0.15
- Ref Proportion 0.25
- N per group: 104

According to these hypotheses the required number of participants per study arm was 104. Hence 220 participants, 110 per group, had to be included.

## 4 ANALYSIS POPULATIONS

In the study protocol the analysis populations were not defined.

As for the safety analyses

the **Safety population**, defined as all the subject who assumed at least one dose of the product, will be considered for the safety analyses.

As for the efficacy analyses

The **Intention-To-treat** population, defined as all the subjects who assumed at least one dose of the study product and had at least one observation after the baseline, will be considered for all the other analyses.

The **Per-Protocol** population, defined as all the subjects that completed all the visits.

The **Per-Protocol V7** population (see DRM Minute in Appendix 5), defined as all the subjects that completed all the visits, included the Follow-up visit (Visit 7).

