### **Inclusion criteria:**

Subjects must meet all of the following inclusion criteria to be eligible for enrolment into the study:

1. Able to comply with the study procedures

2. Male or female healthy smokers aged  $\geq 19$
3. Smoking at least 10 cigarettes a day
4. Smoking for at least one year
5. Not currently attempting to quit smoking or wishing to do so in the next 30 days (this will be verified at screening by the answer “NO” to both questions “Do you intend to quit in the next 30 days?” and “Are you interested in taking part in one of our smoking cessation programs?”)
6. Female smokers not planning to become pregnant are using an acceptable form of contraception.

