## 5 GENERAL INFORMATION FOR THE ANALYSES

	
e-CIG VS. IQOS Statistical Analysis Plan Version 2.0
	Doc code: BIOSTAT.SAP.02
		Pag. 10 of 115

According to the study protocol the statistical analysis will be descriptive in nature.

All the data will be described using standard descriptive statistics, i.e. n, missing, mean, standard deviation, (25th, 50th, 75th) percentiles for numerical variables. As for the categorical variables, frequency tables with count and percentage will be used. In the core of the Statistical Report, the continuous variables will be presented as mean values  $\pm$  standard deviation (SD) or median value and interquartile range [IQR], and categorical variables as numbers and percentages. The descriptive analyses will be presented by group. As indicated in the study protocol, for the primary endpoint, the quit rate at 3 months in the experimental study group will be calculated with a non-inferiority threshold of 15%. The quit rates will be evaluated on an intention-to-treat basis: subjects known to have failed will be considered as treatment failures in the primary analysis along with subjects lost to follow-up.

All the analyses will be performed using SAS® Vers. 9.4.

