### **5.1 Premature discontinuation and missing data managing**

Patients with missing values will not be excluded from the analysis, their data will not be replaced; frequency of missing data will be given for all analyzed variables. For possible inferential analyses, the LOCF (Last Observation Carried Forward) will be adopted.

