## 9.7 Decision taken during the DRM

As described in the Minute included in Appendix 5, on the 10th June 2020 the Data Review Meeting of the study was held in call conference manner. All the decision taken were reported in the Minute. The main decision regarded the analysis population definition. All the protocol violations were evaluated, therefore the following populations were approved by the team:

Population **Safety**: 220

	e-CIG VS. IQOS Statistical Analysis Plan Version 2.0	Doc code: BIOSTAT.SAP.02
		Pag. 21 of 115

Population **Intention-To-Treat**: 217

Population **Per-Protocol**: 193

Population **Per-Protocol V7**: 177

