**3 – Uscita prematura dallo studio**

Per definizione, tutti i soggetti “drop-out” a Visita 6 sono da ritenersi violatori MAGGIORI. Tutti i soggetti che escono dallo studio dopo Visita 2 sono stati esclusi solo dalla popolazione Per-Protocol. I soggetti che escono dallo studio dopo Visita 1 sono stati esclusi anche dalla popolazione ITT.

Nalla call del 22 Giugno è stato deciso di considerare una seconda popolazione PP, la “Per-Protocol V7”, composta da tutti i soggetti, non violatori, che completano anche la visita di follow-up (Visita 7).

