#### **2.4 Scelta del metodo di replicazione dei valori mancanti**

Per l'analisi inferenziale degli endpoint a risposta, il soggetto drop-out è per definizione un "non Responder" (non quitter/failure). Per gli altri endpoint, come riportato nel Capitolo 5.1 del SAP, il metodo di replicazione dei dati mancanti sarà il LOCF (Last Observation Carried Forward).

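### The SAP's intention-to-treat set drops three dosed participants whom the stated primary rule would count as failures

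*SAP*

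**What the plan says.** The rule for the primary endpoint is in the protocol (Statistics, Primary study endpoint). The analysis is by intention to treat, and "subjects known to have failed will be considered as treatment failures in the primary analysis along with subjects lost to follow-up". SAP section 5 repeats it: "The quit rates will be evaluated on an intention-to-treat basis: subjects known to have failed will be considered as treatment failures", again together with those lost to follow-up.

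SAP section 4 notes that the protocol defined no analysis populations and supplies its own. Safety requires one dose. Intention-To-Treat is "defined as all the subjects who assumed at least one dose of the study product and had at least one observation after the baseline". SAP section 7 runs the primary and secondary endpoints on the ITT and PP sets only.

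The data review meeting (DRM) minute in SAP Appendix 5 shows the definition in use. Under the item on premature exit: "I soggetti che escono dallo studio dopo Visita 1 sono stati esclusi anche dalla popolazione ITT", that is, those who left after Visit 1 were removed from ITT as well. Those who left after Visit 2 were removed from the per-protocol set only. SAP section 9.7 records "Population Intention-To-Treat: 217" beside a Safety population of 220.

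Two passages deal with missing data. SAP 5.1 says "Patients with missing values will not be excluded from the analysis, their data will not be replaced", and names LOCF for any inferential analysis. DRM minute 2.4 says that for response endpoints "il soggetto drop-out è per definizione un" non-responder, and keeps LOCF for the other endpoints.

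**The concern.** Someone who takes the product at Visit 1 and never returns is lost to follow-up in the plainest sense. The failure rule is written for that person, but the population definition removes them before the rule can act. Two participants with the same unknown week-12 status are then treated differently according to when they stopped attending: one is a failure, the other is absent from the denominator.

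The trial is open label, and participants try the allocated product for 30 minutes to 2 hours at Visit 1. A decision to leave after that visit is made with knowledge of the arm and experience of the product, so the exclusion could be related to arm. What is at stake is whether the headline non-inferiority result comes from the analysis that the protocol promised.

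**Working it through.** **1. Who is excluded.** Safety and ITT both require one dose; ITT adds the post-baseline observation. Safety 220 − ITT 217 = 3 (3/220 = 1.4%). As all 220 took product, only the added condition can remove the three, and the DRM minute confirms that they left after Visit 1.

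**2. Whether a missing-data rule requires the exclusion.** None does. Counting missing as failure needs no post-baseline value. If LOCF were used and carried the Visit 1 value, it would carry a current smoker (inclusion criterion: "Smoking at least 10 cigarettes a day"), which is also not quit.

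**3. The plan's sample size.** Inputs from the protocol: reference rate 0.25, no true difference, margin 0.15, one-sided alpha 0.05, power 0.80. The Farrington-Manning restricted rates under the null are 0.189 and 0.339.

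- s0 = √(0.189×0.811 + 0.339×0.661) = 0.614
- s1 = √(2×0.25×0.75) = 0.612
- n = [(1.645×0.614 + 0.842×0.612)/0.15]² = 103.5, rounded up to 104 per arm

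The stated 104 reproduces. Power is Φ[(0.15√n − 1.645×s0)/s1]: 82.1% at n = 110 and 81.6% at n = 108.5, the average arm size with 217. Lost power is therefore not the issue.

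**4. Shift in a quit rate.** If all three come from one arm at a 25% rate: 0.25×110/107 − 0.25 = 0.0070, or 0.7 points.

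**5. Effect on the test.** Assumptions: 110 randomised per arm; retained quitter counts unchanged, so the three are non-quitters; Farrington-Manning test, margin 0.15, one-sided 0.05. False non-inferiority is computed exactly, with HnB quitters binomial on n1 with probability p1×110/n1 and EC quitters binomial on n2 with probability p2×110/n2. The arm split is not given, so all four are shown.

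| Lost HnB/EC | False NI, 10% vs 25% | False NI, 5% vs 20% | Conclusion differs, both 25% | Conclusion differs, both 20% |
|---|---|---|---|---|
| none (all 220) | 5.0% | 4.8% | – | – |
| 3/0 | 5.4% | 5.3% | 2.2% | 1.4% |
| 2/1 | 4.9% | 4.8% | <0.01% | <0.01% |
| 1/2 | 4.3% | 4.1% | 2.0% | 1.6% |
| 0/3 | 3.7% | 3.6% | 4.5% | 3.1% |

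Across the 29 EC quitter counts from 16 to 44, the smallest HnB count that passes changes at 16, 4, 14 and 27 of them, in the order of the table. The change is one quitter (two at EC counts 30, 38, 39 and 40 in the 0/3 split). It makes passing easier for HnB in the first two splits and harder in the last two.

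**6. Near-margin examples (one-sided p).**

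- 27/110 HnB vs 33/110 EC: p = 0.0550. With all three lost from HnB, 27/107 vs 33/110: p = 0.0448.
- 22/110 vs 28/110: p = 0.0456. With all three lost from EC, 22/110 vs 28/107: p = 0.0615.
- Away from the margin, 28/110 vs 28/110: p = 0.0054. On 217 it ranges from 0.0041 to 0.0083, and nothing changes.

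**The case against.** The strongest reply is that this is a disclosed and recognisable modified-ITT set and that three people hardly matter. The SAP says that the protocol defined no populations, supplies a definition, and reports the counts and the reason. If each of the three were equally likely to come from either arm, the splits would have weights 1/8, 3/8, 3/8, 1/8. The average false non-inferiority rate would then be about 4.6% at 10% vs 25%, slightly below the 5.0% with all 220. The average chance of a changed conclusion would be about 1.6% with both rates at 25%. The error rates also depend on treating the three as certain failures. If the retained participants themselves have the null rates, the test keeps its size at 4.9% to 5.0% for 10% vs 25%, and at 4.7% to 5.0% for 5% vs 20%. On that view the exclusion changes the quantity estimated and the test itself is sound.

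All of that stands as a statement of size, and it is why the effect is called small. It does not remove the mismatch. The protocol named no sets, but it did fix how those lost to follow-up count, and SAP section 5 says that it follows that rule. A modified set may be used, but it should not carry the ITT name under a rule that it does not apply.

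Two further points are fair. The sentence in SAP 5.1 about not excluding patients with missing values may concern only data within a defined set, so the case rests on the protocol and SAP section 5. DRM minute 2.4 has already taken LOCF away from response endpoints, so the LOCF remark in step 2 is supplementary. That minute does not cure the exclusion, because its failure rule acts only within the 217.

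**Conclusion.** The concern holds. The SAP section 4 definition conflicts with the primary rule in the protocol and in SAP section 5, and the conflict was realised: three dosed participants are left out of the primary analysis. The numerical effect is minor and can alter only results close to the margin. Its direction cannot be known until the arms of the three are shown, which mock Table D.1 should allow. The figures assume 110 randomised per arm; the documents give 220 as the planned number and as the Safety count, but do not state the number randomised. The sample size is not in error. This should be corrected because the stated rule and the analysed set ought to agree, and not because a large bias is expected.

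**What to change.** For the quit-rate tables (E.1a, E.1b and E.2b), define ITT as all randomised participants, analysed in the arm to which they were randomised, with missing status at the time point counted as not quit. Confirm and state the number randomised. The reduction table (E.2a) can use the same set, noting that its failure rule comes from DRM minute 2.4 and not from the protocol.

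Rename the 217-person set modified ITT, keep it as a sensitivity analysis, and report how many it leaves out per arm. Reword SAP 5.1 to agree with DRM minute 2.4, so that LOCF plainly does not apply to response endpoints.

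The cost is SAP wording and one re-derived population flag. Reported quit rates would fall slightly, within the limit worked out in step 4.
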